#### **7.1.4. Relationship of Adverse Events to Study Procedure**

Study procedure related AEs are those for which the investigator selected “Yes” on the AE CRF to the question of “Related to Study Procedures.” Relatedness will always default to the investigator’s choice, not that of the medical monitor. Events for which the investigator did not record relationships to study procedure will be shown as missing from that captured on the CRF in by-subject data listings.

#### **7.1.5. Serious Adverse Events**

Serious adverse events (SAEs) will be identified and captured as SAEs if AEs met the definitions of SAE that were specified in the study protocol. SAEs captured and stored in the clinical database will be reconciled with the SAE database from the Gilead Pharmacovigilance and Epidemiology (PVE) Department before database finalization.

## **7.1.6. Treatment-Emergent Adverse Events**

### **7.1.6.1. Definition of Treatment-Emergent Adverse Events**

Treatment-emergent adverse events (TEAEs) are defined as one or both of the following:

- Any AEs with an onset date on or after the study drug start date and no later than 30 days after permanent discontinuation of study drug
- Any AEs leading to premature discontinuation of study drug

### **7.1.6.2. Incomplete Dates**

If the onset date of the AE is incomplete and the AE stop date is not prior to the first dosing date of study drug, then the month and year (or year alone if month is not recorded) of onset determine whether an AE is treatment emergent. The event is considered treatment emergent if either of the following 2 criteria is met:

- The AE onset and end dates are the same as or after the month and year (or year) of the first dosing date of study drug
- The AE onset date is the same as or before the month and year (or year) of the date corresponding to 30 days after the date of the last dose of study drug

An AE with completely missing onset and stop dates, or with the onset date missing and a stop date later than the first dosing date of study drug, will be considered to be treatment emergent.

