8.6.2. Adverse Events

Clinical and laboratory adverse events will be coded using the Medical Dictionary for Regulatory Activities (MedDRA). System Organ Class (SOC), High-Level Group Term (HLGT), High-Level Term (HLT), Preferred Term (PT), and Lower-Level Term (LLT) will be attached to the clinical database.

Treatment-emergent AEs are 1) any AEs with onset date on or after the study drug start date and no later than 30 days after the study drug stop date, or 2) any AEs leading to study drug discontinuation.

Summaries (number and percentage of subjects) of treatment-emergent adverse events (by SOC and PT) will be provided by treatment group. Additional summaries will include summaries for adverse events by grade, Investigator's assessment of relationship to study drug, and effect on study drug dosing.

On an ongoing basis adverse events will be reviewed for events that might meet the definition of Category C events that are indicative of an AIDS-Defining Diagnoses. The Gilead medical personnel will review the possible Category C events and approve the events that meet the definition. Those events that do meet the Category C definition of an AIDS-Defining Diagnosis will be listed.

A listing of Category C, AIDS-Defining Diagnosis can be found in [Appendix 6](#).

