### **3.6. Missing Data and Outliers**

#### **3.6.1. Missing Data**

A missing datum for a given study analysis window may be due to any of the following reasons:

- A visit occurring in the window but data were not collected or were unusable
- A visit not occurring in the window
- A subject prematurely discontinuing from the study before reaching the window

In general, values for missing data will not be imputed, unless methods for handling missing data are specified.

The handling of missing or incomplete dates for AE onset is described in Section 7.1.6.2, and for concomitant medications in Section 7.4.

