### Appendix 3. Programming Specification

- 1) AGE calculated as follows:
  - a) AGE (years) is calculated from the number of days between the date of birth (DOB) and Day 1 (first dose date),
  - b) Use the SAS INTCK function to determine the number of “1st-of-month days” (eg, January 1st, February 1st, March 1st) between DOB and Day 1 (inclusive),
  - c) Divide the result in (b) by 12,
  - d) AGE = the integer of the result in (c),
  - e) If the DOB and Day 1 have the month in common and the birthday is later in the month than the date of Study Day 1, then subtract one from the AGE result above.

For subjects randomized and never dosed with study drug, age will be calculated from the date of randomization.

- 2) All screened subjects refer to all subjects who are screened (ie, with nonmissing screening date) and have a screening number. For summaries, the same subject is counted only once. DOB and other demographic information such as sex, race, ethnicity, country, and initials will be used to identify unique screened subjects.
- 3) Screen failure subjects are the subjects who are screened and answered “No” for any inclusion criteria or “Yes” for any exclusion criteria regardless of which version of protocol the subject was consent to.
- 4) Subjects in the randomized analysis set are defined as subjects randomized into the study. IXRSRAND is the source to determine whether the subject is randomized (ie, subject with nonmissing RGMNDTN in the IXRSRAND dataset) and confirmed by the eCRF ENROLL dataset (ie, ENROLLYN = “Yes” in ENROLL dataset).
- 5) Randomized treatment (ie, TRT01P in ADSL) are derived from IXRSRAND, while actual treatment received (ie, TRT01A in ADSL) is assigned as the randomized treatment if subject took at least 1 dose of study drug and assigned as blank if subject never dosed.
- 6) In disposition table, the reasons for premature discontinuation are displayed in the order as they appear on the eCRF.

7) Body mass index (BMI) and Body Surface Area (BSA)

BMI and BSA will be calculated only at baseline as follows:

$$\text{BMI} = (\text{weight [kg]}) / (\text{height [meters]}^2)$$

$$\text{BSA (m}^2\text{)} = \text{SQRT}([ \text{Height(cm)} \times \text{Weight(kg)} ] / 3600 )$$

Baseline height and weight will be used for this calculation.

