**Events with Missing Onset Day and/or Month**

An AE is treatment emergent if the following 3 criteria are met:

- The month and year (or year) of onset date is the same as or after the month and year (or year) of the first dose of study drug, and
- The month and year (or year) of the onset date is the same as or before the month and year (or year) of the 30th day after the date of the last dose of study drug, and
- End date is as follows:
  - a. The (complete) end date is on or after the first dose date, or
  - b. The month and year (or year) of end date is the same or after the month and year (or year) of the first dose of study drug, or
  - c. End date is completely missing

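### SAP 7.1.6.2 makes a partially dated adverse event treatment-emergent if either date bound is met; the definition itself and SAP Appendix 3 require both

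*SAP*

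**What the plan says.** The definition has two limbs. On dates, SAP 7.1.6.1 asks for an "onset date on or after the study drug start date and no later than 30 days after permanent discontinuation of study drug", and protocol 8.6.2 for an "onset date on or after the study drug start date and no later than 30 days after the study drug stop date". Separately, both count events that lead to stopping study drug, whatever their onset date ("Any AEs leading to premature discontinuation of study drug" in the SAP; "any AEs leading to study drug discontinuation" in the protocol).

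For incomplete onset dates the SAP gives two rules:

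- **Section 7.1.6.2** applies when the stop date is not before first dose: "The event is considered treatment emergent if either of the following 2 criteria is met". Criterion 1 is that onset and end fall in or after the month and year of first dose. Criterion 2 is that onset falls in or before the month and year of last dose plus 30 days. If the month is unknown, years are compared.
- **Appendix 3, item 11**: "An AE is treatment emergent if the following 3 criteria are met". These are the same lower bound, the same upper bound and an end-date condition, joined by *and*. A completely missing end date satisfies the end-date condition.

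Each rule has a claim to govern. SAP 3.6.1 states: "The handling of missing or incomplete dates for AE onset is described in Section 7.1.6.2". The other rule sits under the title "Appendix 3. Programming Specification".

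**The concern.** The two criteria in 7.1.6.2 are the two ends of one interval. Joining them with *either* turns a test for lying inside the interval into one that almost any date passes. An event whose recorded onset month is before first dose, and which lasted into the dosing period, would be called treatment-emergent on the upper bound alone, against the definition in 7.1.6.1. At the other end, an event whose onset month is after the 30-day window would be called treatment-emergent on the lower bound alone.

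The incidence of treatment-emergent serious and all adverse events is the primary safety endpoint (protocol 8.1.2). The high-level table in SAP 7.1.7 is built on the flag, and the listing of all adverse events carries it as a variable. Two programmers, one working from the body of the SAP and one from Appendix 3, could derive different flags from the same data.

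**Working it through.** The plan gives no figure to reproduce; the point is one of logic.

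**Step 1: the rule as written.** Let F be the month of first dose and U the month of last dose plus 30 days, so F ≤ U. Let m be the recorded onset month. Suppose the end date is known and, as 7.1.6.2 requires, not before first dose. Criterion 1 then reduces to m ≥ F, and criterion 2 is m ≤ U.

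- If m < F, then m < F ≤ U, so criterion 2 is met.
- If F ≤ m ≤ U, both are met.
- If m > U, then m > U ≥ F, so criterion 1 is met.

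*Either* therefore excludes nothing beyond the stop-date precondition; *both* gives F ≤ m ≤ U. If a missing end date is read as failing criterion 1, the only unflagged events are those with a missing end date and m > U. The argument for years is the same.

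**Step 2: one case.** Assume first dose on 10 June 2018 and ten doses 14 days apart. Last dose is 9 × 14 = 126 days later, 14 October 2018; adding 30 days gives 13 November 2018. An event starting in May 2018 (day unknown) and ending on 20 June 2018 fails criterion 1 (May is before June) but meets criterion 2 (May is before November). Section 7.1.6.2 flags it; Appendix 3 does not.

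**Step 3: all month combinations.** The rules were run over onset months from four before F to four after U, with every end month up to six after U or a missing end date. A second example assumed first dose on 15 March 2017 and six doses (last dose 24 May, plus 30 days 23 June 2017). These are counts of date combinations, not expected events.

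| Onset month (stop not before first dose) | 7.1.6.2, ten / six doses | Appendix 3, ten / six doses |
|---|---|---|
| Before F | 52 of 52 / 44 of 44 | 0 / 0 |
| F to U | 63 of 63 / 38 of 38 | 63 of 63 / 38 of 38 |
| After U | 22 of 22 / 22 of 22 (18 of 22 in each if a missing end date fails criterion 1) | 0 / 0 |

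A further 10 pre-dose combinations in each example stopped before the first-dose month; neither rule flags them.

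**Step 4: how often the rules would differ for a pre-dose event.** Assume first dose is equally likely on any day of a 365-day year and the event persists to first dose. Day −k is k days before first dose (SAP 3.8.1). The rules differ when the onset falls in an earlier calendar month than first dose (day missing) or an earlier year (day and month missing).

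| True onset | Day missing | Day and month missing |
|---|---|---|
| Day −1 | 12/365 = 3.3% | 1/365 = 0.3% |
| Day −7 | 84/365 = 23.0% | 7/365 = 1.9% |
| Day −13 | 156/365 = 42.7% | 13/365 = 3.6% |
| Day −30 | 358/365 = 98.1% | 30/365 = 8.2% |
| Day −31 | 365/365 = 100% | 31/365 = 8.5% |
| Day −48 | 365/365 = 100% | 48/365 = 13.2% |

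For k up to 28 the first column is 12k/365, because the first k days of each month are affected; the second is k/365. The counts are the same for 2017, 2018 and 2019 and for both dosing schedules.

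**Step 5: effect on a table row.** Each active arm plans 6 subjects, and pooled placebo 6 cohorts × 2 = 12. One reclassified subject adds 1/6 = 16.7 or 1/12 = 8.3 percentage points, and only if that subject has no other event in the row.

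**Step 6: is changing one word enough?** Not quite. With *both*, all pre-dose and post-window combinations drop out. But if a missing end date fails criterion 1, 6 of 63 and 4 of 38 in-window combinations that Appendix 3 keeps are lost. The end-date wording must change too.

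**The case against.** The strongest reply is that the intended rule is clear and hardly any event is affected.

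On intent, 7.1.6.1, protocol 8.6.2 and Appendix 3 all require both bounds, and SAP 7.7 says that the safety analyses do not depart from the protocol. That shows which reading was meant, but it does not settle the conflict. Section 7.7 says nothing about partial dates, SAP 3.6.1 points to 7.1.6.2, and programming that section would make the statement in 7.7 untrue.

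On reach, the reply largely stands. The event must start between consent and first dose, still lack an onset day at final analysis, and not have stopped before dosing. Before dosing only serious and procedure-related events go on the adverse event form (protocol 6.2 and 7.3). Serious events are transmitted within 24 hours and reconciled with the safety database, and data discrepancies are queried. Protocol 8.6 sends pretreatment data to listings, and SAP 3.1.3 and 3.8.2 limit late data in summaries. A wrong flag may therefore reach only a listing. SAP 3.1.3 states no lower limit, however, so a subject could enter a summary row if the flag selects the records.

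Bias between arms is unlikely, since allocation is randomised and blinded and SAP 7.1.7 plans no test on adverse events.

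Two cautions on the figures are fair. The percentages in step 4 apply only once a partially dated pre-dose event that persists to dosing exists; they are not error rates. The 16.7 points assume six subjects dosed; with five it would be 1/5 = 20.

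A bare cross-reference to Appendix 3 has also been suggested. It would work only if the conflicting criteria in 7.1.6.2 were deleted as well.

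**Conclusion.** The concern holds. SAP 7.1.6.2 is wrong as written: beyond its stop-date precondition it excludes no event with a known end date, and it contradicts Appendix 3 item 11 and the date limb of the definition in both documents. The error occurs if 7.1.6.2 is programmed and is avoided if Appendix 3 is. Events that stopped before first dose, and events that led to stopping study drug, are classified correctly either way.

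The effect is probably small but cannot be sized, because the number of partial onset dates is not given. The correction should still be made, because the flag defines the primary safety endpoint and the change costs almost nothing.

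There is one minor mismatch for a wholly missing onset date: 7.1.6.2 needs a stop date after first dose, whereas Appendix 3 accepts one on that date. With a complete stop date the two differ only for an event that stopped on the day of first dose.

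**What to change.** Edit SAP 7.1.6.2:

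1. Require *both of the following criteria* in place of either.
2. Limit criterion 1 to the onset date, and add the end-date condition from Appendix 3 item 11 (a to c), including a completely missing end date.
3. Add a sentence that events leading to premature discontinuation of study drug remain treatment-emergent under 7.1.6.1 whatever their onset date. This restates the existing definition so that the stricter date rule cannot be misread.
4. As minor alignment, in the last paragraph accept a stop date *on or after* the first dosing date (or the same month and year or later, if the stop date is partial).

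The cost is four short wording edits. Appendix 3 item 11 stays as it is, and no new data are needed.

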## **7.1.7. Summaries of Adverse Events and Deaths**

A brief high-level summary of TEAEs will be provided by treatment for the number and percentage of subjects who had the following: any TEAE; any TEAE of Grade 3 or above; any serious TEAE; any study drug-related TEAE; any study drug-related serious TEAE; any TEAE that led to premature discontinuation of study drug. The treatment-emergent deaths observed during the study will also be summarized and included in this table. Treatment-emergent death refers to the death occurred between the first dose date and the last dose date plus 30 days, inclusive.

Adverse event summaries will provide the number and percentage of subjects with AEs by SOC and PT, by treatment based on the Safety Analysis Set as follows:

- All AEs
- All AEs by severity
- AEs of Grade 3 or above
- All study-drug related AEs

- All SAEs
- All study-drug related SAEs
- All AEs leading to premature discontinuation of study drug

Multiple events will be counted only once per subject per treatment in each summary. An AE that starts in one treatment period and continues into the following treatment period(s) will be counted only in the period in which the AE began. Adverse events will be summarized and listed first in alphabetic order of SOC and then by PT in order of descending incidence of the pooled treatment groups within each SOC. For summaries by severity, the most severe grade will be used for those AEs that occurred more than once in an individual subject per treatment during the study.

In addition to the by-treatment summaries described above, data listings will be provided for the following:

- All AEs (with a variable indicating whether the event is treatment emergent)
- SAEs
- Deaths
- AEs leading to premature discontinuation of study drug

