Safety: AEs and clinical laboratory tests will be collected at every visit and summarized through Day 101 or Day 157 (30 days after the last dose of GS-9620 or placebo).

The following are DLTs:

- ALT elevation defined as:
 - $ALT \geq 10 \times ULN$ **OR**
 - confirmed ALT elevation (i.e. grade shift or $2 \times$ previous value) with evidence of worsened hepatic function (e.g. total bilirubin > 2 mg/dL above Baseline, serum albumin > 1 g/dL decrease from Baseline)
- A confirmed \geq Grade 3 AE considered by the investigator to be study drug-related

- A confirmed \geq Grade 3 lab abnormality considered by the investigator to be study drug-related and clinically significant
- A persistent (≥ 72 hours) \geq Grade 2 flu-like symptom (eg pyrexia, fatigue, myalgia, arthralgia, headache, chills) considered by the investigator to be study drug-related
- A post-dose increase in plasma HIV-1 RNA that fails to resolve to < 50 copies/mL within 10 days in Cohorts 1 to 3
- A post-dose increase in plasma HIV-1 RNA that fails to resolve to < 200 copies/mL within 10 days in Cohorts 4 to 9

The Investigator will notify the SEC within 24 hours of any DLT. The SEC may unblind the treatment assignment for a subject experiencing a DLT.

Study drug dosing for a subject may be discontinued if the subject receives GS-9620 and experiences one or more DLTs considered to be related to study drug.

A Dose Cohort may be discontinued if ≥ 2 out of 6 subjects receiving GS-9620 experience one or more DLTs considered related to study drug.

Statistical Methods:

Safety:

To evaluate overall safety, the incidences of treatment-emergent AEs and treatment-emergent laboratory abnormalities will be summarized by treatment group.

The proportion of subjects in each treatment group with an AE leading to premature discontinuation of study drug and proportion of subjects with serious adverse events (SAEs) will be summarized by treatment group.

Virology:

The change in plasma HIV-1 RNA and the incidence of detectable plasma HIV-1 RNA at each visit will be summarized by treatment group.

The change in plasma HIV-1 RNA SCA from pre-dose to 2 days post-dose may be explored.

The change in cell (PBMC) associated HIV-1 RNA from pre-dose to 2 days post-dose may be explored.

The change in HIV-1 reservoir measured by cell (PBMC) associated HIV-1 DNA from pre-dose to 2 days post-dose, and in Cohorts 4 to 9 by use of secondary assays using stored PBMC samples may be explored

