7.6.2.2. Grade 3 Laboratory Abnormality or Clinical Event

- For a Grade 3 clinical event or clinically significant Grade 3 laboratory abnormality confirmed by repeat testing, IMP should be withheld until the toxicity returns to \leq Grade 2.
- If a laboratory abnormality recurs to \geq Grade 3 following rechallenge with IMP, then IMP should be permanently discontinued and the subject managed according to local practice.

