#### **7.1.8. Additional Analysis of Adverse Events**

No additional analysis of adverse events is planned.

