## **7.7. Changes From Protocol-Specified Safety Analyses**

There are no deviations from the protocol-specified safety analyses.

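### The SAP narrows the protocol's AE summaries by effect on dosing to discontinuation alone and omits the Category C listing, yet declares no deviation

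*SAP*

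**What the plan says.** Protocol 8.6.2 says that, beyond the SOC and preferred-term tables, additional AE summaries will be given by grade and by the investigator's "assessment of relationship to study drug, and effect on study drug dosing". The same section has sponsor medical staff review possible AIDS-defining events and then commits to an output: "Those events that do meet the Category C definition of an AIDS-Defining Diagnosis will be listed".

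SAP 7.1.7 specifies an overview table, seven SOC/PT tables and four listings. Each contains one entry on dosing, and it is always permanent discontinuation: the overview counts "any TEAE that led to premature discontinuation of study drug", and the SOC/PT tables include "All AEs leading to premature discontinuation of study drug", with a matching listing. For the listing of all AEs, the only added variable named is a treatment-emergent flag. Category C events are not mentioned. SAP 7.1.8 then says "No additional analysis of adverse events is planned", and SAP 7.7 says "There are no deviations from the protocol-specified safety analyses".

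**The concern.** Safety and tolerability of escalating doses is a primary objective. In this protocol a toxicity acts on dosing mainly by withholding it. After any DLT, dosing is held until the SEC decides what happens next (7.6.1). A Grade 3 clinical event, or a confirmed and clinically significant Grade 3 laboratory abnormality, leads to a hold until the grade falls (7.6.2.2). Restart at full or modified dose is foreseen (7.6.2). Protocol 7.1.3 treats interruption, modification and discontinuation of study drug as three separate consequences of a laboratory abnormality.

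If the outputs identify only permanent discontinuation, a reader of the clinical study report cannot tell from them how many subjects at a given dose had dosing held because of an AE and later resumed. That is a direct measure of tolerability, and the protocol promised it. A reader who relies on SAP 7.7 would also believe that every protocol-specified safety output is present.

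**Working it through.** The plan gives no figure to reproduce, so the check compares the texts and then follows individual events through the planned outputs.

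**Commitment against delivery**

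| Protocol commitment | SAP provision |
|---|---|
| AE summaries by grade (8.6.2) | SOC/PT tables by severity and for Grade 3 or above: met |
| AE summaries by relationship to study drug (8.6.2) | Related-AE and related-SAE tables: met |
| AE summaries by effect on dosing (8.6.2) | Premature discontinuation only: met in part |
| Listing of confirmed Category C events (8.6.2) | None named: not met |

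**Count of SAP 7.1.7 outputs**

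- Overview table: six TEAE categories plus deaths. One concerns discontinuation; none concerns a withheld, delayed or modified dose.
- SOC/PT tables: seven. One concerns discontinuation; none concerns a withheld, delayed or modified dose.
- Listings: four (all AEs, SAEs, deaths, AEs leading to discontinuation). None is specific to holds, and no action-taken variable is named.

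**Where an event that caused a hold would appear**

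- *Related Grade 2 flu-like symptom lasting 72 hours or more.* This is a DLT, so dosing is withheld (Protocol 7.6.1). It is counted in the all-AE, severity and related tables. It does not reach the Grade 3 or above table, nor the discontinuation table if dosing resumes. In the tables it looks the same as a brief related Grade 2 symptom that left dosing unchanged.
- *Grade 3 event held and then resumed.* It is counted in the all-AE, severity and Grade 3 or above tables, and in the related or serious tables where it qualifies. The hold is not shown.
- *Confirmed Grade 4 event related to study drug.* Protocol 7.6.2.3 calls for permanent discontinuation, so it reaches the discontinuation table. There is no gap here.
- *Grade 3 or 4 event recurring after an interruption.* Protocol 7.6.2 calls for permanent discontinuation, so the recurrence is captured.
- *Hold for viremia (Protocol 6.8.1).* Whether this enters any AE output depends on whether it is recorded as an AE. The point does not rely on it.

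**Other routes to the same information**

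- SAP Section 7 plans no DLT table.
- Protocol 8.6.1 commits to summarizing exposure by treatment group; SAP 4.2 only lists it. This is a further departure that SAP 7.7 does not declare. The protocol's own duration measure ignores temporary interruptions, so even that summary of duration would not show held doses.

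**Scale, for illustration only**

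Each dose group has 6 active subjects. One held-then-resumed subject is 1/6 = 16.7% of the group, and two are 2/6 = 33.3%. These figures show what one or two subjects represent; they do not estimate how often holds occur or any bias.

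**The case against.** The strongest reply is that the commitment is loosely worded. The protocol never defines the categories of dosing effect, and its synopsis promises only the "proportion of subjects in each treatment group with an AE leading to premature discontinuation of study drug", together with SAEs. The SAP tables match the synopsis. This has some force: the discontinuation outputs do meet part of the commitment. But a shorter synopsis does not cancel an explicit sentence in 8.6.2. That section names discontinuation specifically in its TEAE definition, so its broader phrase is most naturally read as covering more.

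Second, the information may be recoverable. All AEs and all exposure data are listed by subject, the SAP does not say that its named listing variables are exhaustive, and with six active subjects per dose a reader could align the two listings. That is possible, but the eCRF and table shells are not available to confirm it, and a listing that must be reconstructed is not the promised summary.

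Third, holds may be rare. Protocol 1.4 reports no DLTs through 6 mg, and no Grade 3 or 4 AEs or AE-driven discontinuations at 6 mg or, at the interim cut, at 8 mg. Doses are also 14 days apart, so a short-lived event may resolve before the next dose is due. This limits the likely size of the gap but does not remove the mismatch.

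A reader might also draw stronger conclusions, which the documents do not support:

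- *That AEs causing a hold disappear from the tables.* They do not; SAP 7.1.7 still counts them in the all-AE and severity tables and in others where they qualify. Only the fact of the hold is missing.
- *That a 0% discontinuation row would misreport a subject who was held and then resumed.* It would be correct, since that subject did not discontinue. No planned table reports holds as 0%.
- *That the loss is known to be greatest at the top doses.* Protocol 1.2.3.1 reports more flu-like symptoms at 8 and 12 mg in healthy volunteers, which makes this plausible, but the documents contain no 10 or 12 mg results from this study.

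Finally, the Category C listing has nothing to do with dose holds, and such events would still be in the all-AE listing. That is true. It belongs here because it is a separate output promised in the same protocol section, and it also makes SAP 7.7 untrue.

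**Conclusion.** The mismatch stands. Following the SAP exactly would drop part of one protocol-specified AE output and the whole of another, and SAP 7.7 is incorrect in declaring no deviation. Holds remain unidentified even though they bear on a primary objective. The clearest case is the persistent related Grade 2 flu-like symptom, which is dose-limiting by definition yet cannot be told apart in the tables from a brief one.

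The consequence is an incomplete tolerability display and an inaccurate declaration. It does not bias any planned estimate, and its size cannot be computed from the documents. The conclusion assumes that effect on dosing in Protocol 8.6.2 covers more than discontinuation, which is the natural reading though not a defined one. The design needs no change, but the point should be settled before the SAP is finalized.

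**What to change.** In SAP 7.1.7:

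- add an overview row for TEAEs leading to interruption, delay or modification of study drug;
- add a summary of these TEAEs by treatment group, in the SOC/PT format of the other tables;
- add a by-subject listing that shows which dose number was affected;
- add the listing of confirmed Category C events.

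If the sponsor prefers not to produce these, SAP 7.7 should declare each omission as a change from Protocol 8.6.2 and justify it. In either case SAP 7.7 should also cover the exposure summary in Protocol 8.6.1, unless that summary is restored in SAP 4.2. If the SAP is already final, SAP Section 1 requires the change to be documented in the clinical study report.

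The cost is one row, one table and two listings: a small amount of extra programming. This assumes that the eCRF collects action taken with study drug for each AE, which the protocol commitment implies but the documents do not show. If it does not, SAP 7.7 should say so.
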